2.2.2 Secondary Outcomes

- Parental report of provider-diagnosed AD - This parental report of AD question has been validated previously by our group and was found to have adequate sensitivity and specificity during our trial planning activities.³⁹

- AD as diagnosed by the Children's Eczema Questionnaire (CEQ) – The CEQ is a newly developed 2-question parental questionnaire based on the U.K. Working Party criteria.⁴⁰ This instrument will be used to capture dyads not evaluated by their provider or lost to follow-up (Appendix A).
- Parental report of sleep loss of the infant reported as average parental report of days per week of disrupted sleep in their infant (1 week recall) measured at 12 and 24 months.
- Any prescription topical medication use or over-the-counter hydrocortisone usage recorded by parent or recorded from records review by research coordinator at 24 months.
- Asthma risk questions from the modified Asthma Predictive Index (mAPI) that uses family history, atopic dermatitis, sensitization history, and wheezing episodes to predict the development of asthma measured by parental report.⁴¹ This will be recorded as either high risk or low-risk at 12 and 24 months following mAPI criteria (Appendix B). Wheezing episodes will be assessed using the International Study of Asthma and Allergies in Childhood (ISAAC) questionnaire.
- Parental report of immediate food allergy symptoms – A general question regarding the development of red rash/hives, lip swelling, wheezing, abdominal pain, or vomiting that developed in the infant within two hours of eating a food.
- Parental report of a provider diagnosis of food allergy that was confirmed by prick testing or IgE blood test.
- One question global health status from the PROMIS Pediatric Global Health (PGH-7) instrument.⁴² (Appendix C)
- In infants who develop AD, a logic model in our survey instrument will ask the following parental reported outcomes in the 12- and 24-month questionnaires:
 1. Time to onset of AD as measured by parental report of eczema age of onset.
 2. Time to onset of AD as measured by provider-recorded date of first diagnosis retrieved from record review of chart by research coordinator.
 3. AD symptom severity as reported by the Patient-Oriented Eczema Measure (POEM) instrument⁴³ (Appendix D).
 4. Parent-reported global severity of eczema assessment – mild, moderate, severe
 5. Infant Dermatology Quality of Life Instrument (IDQOL) – a validated 10-question questionnaire designed for children under 4 years of age⁴⁴ (Appendix E).

3 STUDY DESIGN

3.1 Study Design Overview

This is a pragmatic, multi-site, randomized community-based trial that will enroll dyads of a parent or guardian (“parent”) and an infant who is up to 2 months old. Both high-risk infants (with family history of atopic disease) and average-risk infants (with no family history of atopic disease) will be eligible. Each dyad will be randomized to the intervention arm (daily emollient therapy) or the control arm (encouraged to adhere to current infant skin care guidelines without regular emollient use). Over the course of two years, 1,250 dyads will be enrolled in the trial with 625 dyads assigned to each study arm. It is anticipated that 2,500 dyads will be screened in order to reach the target enrollment.

Once randomized, dyads will participate in the study until the infant is 24 months of age (approximately two year study duration). Parents will complete a questionnaire at enrollment (prior to randomization) and follow-up annual questionnaires when the infant is 12 and 24 months old. Every three months of child’s age (e.g., age 3 months, 6 months, 9 months, etc.), parents will be contacted via e-mail or SMS text message and asked to complete a quarterly survey, have an opportunity to update their contact information, report on adherence to study arm, be given messages about daily emollient use or general infant skin care guidelines and report adverse events and serious adverse events. Finally, two weeks after enrollment into the study, dyads in both arms will receive an e-mail or text message with a brief study message for both arms, with the intervention arm getting an additional message encouraging daily emollient use.

Total study duration will last for five years, with enrollment projected to be completed at the end of study year 2 and data collection projected to be completed at the end of study year 4. After completion of the screening and enrollment, participant-specific links to subsequent questionnaires will be sent by e-mail or SMS text message. Follow-up for incomplete questionnaires, unresponsive participants, as well as for individuals that did not have a valid e-mail address or phone that could not receive text messages may receive additional contact from the Clinical Coordinating Center (CCC).

3.2 Setting

This study will take place in 35 community-based primary care clinics located in four states in the United States: Colorado, North Carolina, Oregon, and Wisconsin. The community-based setting, combined with the multi-regional site selection, will increase the potential for racial and ethnic diversity representative of the U.S. population.

Prior to study implementation, the CCC and PBRN research coordinators will train participating clinic staff on methods for proper diagnosis of AD. PBRN research coordinators will ensure that staff and clinicians who join the study after initial training receive the training materials and complete a test.

3.3 Treatment Arms

There are two arms in the study- intervention and control. Both study arms will receive text messages and e-mail links providing general skin care educational material

throughout the study. This general skin care information includes information regarding the use of gentle cleansers, bathing safety tips and managing rash. All dyads will be reminded of their treatment arm every three months via electronic survey and e-mail. Both arms will be contacted at the same frequency. There are no evidence-based guidelines for frequency of bathing. Because bathing practices vary between families considerably, only general bathing tips will be provided to both groups.

3.3.1 *Intervention Arm*

Dyads assigned to the intervention arm will receive a study-approved emollient of their choice by mail at regular intervals throughout the study and instructed to use the emollient once-daily over the entire body. Parents may avoid the scalp, if needed. Quarterly reminders will be sent during the course of the study instructing parents on the daily use of the study emollient. In addition, the intervention group will receive general infant skin care information identical to the control group.

3.3.2 *Control Arm*

Dyads assigned to the control arm will be instructed to refrain from routine emollient use and only use emollients on an “as needed” basis if their baby develops dry skin. Like the intervention group, dyads in the control arm will also receive general infant skin care guidelines. Information in the control educational materials will include general infant skin care recommendations, such as bathing and rashes. The information in educational materials will be current standard of care for the topics included.

3.4 Rationale for Study Design Elements

3.4.1 *Pragmatic Trial Design*

It is now recognized that the results from traditional randomized controlled trials (RCTs) often do not generate the information necessary to properly inform health care guidelines or policy.⁴⁵ Trial participants often are not representative of the population in which the therapy will be implemented. This discrepancy can lead to well-tested therapies either not working, or to unexpected toxicities, when delivered in a real-world setting. Clinical trials, in contrast to traditional RCTs, are designed to address real-world clinical situations and provide results that are directly applicable to large populations.

3.4.2 *Community-based Setting*

A pragmatic trial using a community-based setting provides several advantages over a traditional RCT in the context of this study. First, by recruiting from primary care and pediatric clinics, we anticipate improved efficiency in enrollment and reduced loss-to-follow-up. Recently, a trial of emollient intervention for AD prevention from Australia could not be performed due to the study only enrolling 5% of their target sample size using a standard RCT approach.⁵⁰ Second, a community-based pragmatic trial design, unlike many RCTs performed in academic centers, allows for the results of the trial to be immediately generalizable to large populations. Trial design better mirrors how the intervention would be implemented in the general primary care community. By generating data regarding the **effectiveness** of this intervention in a community setting,

this trial design provides the best chance that the results of the trial will have the largest public health impact.

3.4.3 Clinician Training in AD Diagnosis

During the first two months of the funded project, all 25 community-based primary care study sites will undergo whole staff protocol training led by the CCC, PI and PBRN research coordinator. Training of all clinicians in performing the primary assessment occurs during this time using a competency-based training module with clinical assessment of AD. Clinicians will be trained in valid and standardized diagnosis using the American Academy of Dermatology (AAD) Consensus Criteria for diagnosing pediatric AD.³⁷

3.4.4 Electronic-based Data Gathering

Parent-derived electronic data gathering greatly improves the overall efficiency of this trial.⁴⁹ Because of the size of the trial population and number of participating sites, traditional study visits with in-person assessments or exclusively over-the-phone contacts would be extremely costly. Electronic data gathering reduces the overall parent burden and clinic burden when participating in the study and greatly reduces the overall cost of the study data management.

4 STUDY ENROLLMENT AND WITHDRAWAL

4.1 Participant Inclusion Criteria

In order to be eligible to participate in this study all of the following criteria must be true for the dyad:

- Parent can provide signed and dated electronic informed consent form
- Parent is willing and able to comply with all study procedures for the duration of the study
- Parent is a primary caretaker of an infant 0 to 2 months of age
- Parent is 18 years of age or older at time of consent
- Parent can speak, read, and write in English or Spanish
- Parent has a valid e-mail address or phone that can receive text messages
- Parent has reliable access to the internet
- Infant is a patient of a participating Meta-LARC clinic site at the time of consent

4.2 Inclusion of Vulnerable Populations

4.2.1 *Inclusion of Women*

All adults, including women, who are at least 18 years of age and who meet inclusion/exclusion criteria will be eligible for study participation. There are no exclusion criteria with regards to gender of the infant.

4.2.2 *Inclusion of Minorities*

All members of racial and ethnic minority groups will be eligible for study participation and no participants will be excluded on the basis of race or ethnicity. All study materials will be provided in Spanish to include Spanish-speaking populations.

4.2.3 *Inclusion of Children*

Via parental consent, infants will be enrolled into this study based on the inclusion and exclusion criteria. In order to prevent AD, interventions directed at the earliest stages of life are needed since the majority of AD begins with the first two years of life. Child assent will not be obtained for this study, as children in the target age group upon enrollment are not developmentally able to provide assent. Informed consent will be obtained by one parent or legal guardian.

4.2.4 *Inclusion of Neonates*

The project will enroll dyads of parents and neonates/infants 0 to 2 months of age with the intervention targeted at parental skin care habits for the infant. Neonates of uncertain viability or nonviable neonates will not be included in this study. Viability will be determined by the fact that the infant is being seen at the outpatient clinic site (i.e. if the infant is a patient at the clinic, they are considered viable).

4.3 Participant Exclusion Criteria

A dyad who meets any of the following criteria will be excluded from participation in this study:

- Infant born at less than 25 weeks gestational age
- Infant has established eczema as diagnosed by the primary healthcare provider at clinic site of enrollment per parent report
- Infant has known adverse reaction to petrolatum-based emollients
- Infant has an immunodeficiency genetic syndrome such as Wiskott-Aldrich Syndrome or Severe Combined Immunodeficiency Syndrome
- Infant has extremely low birthweight (less than 1000g or 2.2 lbs [2 pounds 3 ounces] at birth)
- Infant has a sibling enrolled in the study
- Parent is unwilling or unable to comply with study procedures

4.4 Enrollment Procedures

4.4.1 Screening

Parent/infant dyads will be recruited from 35 PBRN-affiliated primary care offices in four states. Potential dyads will be informed of the study by clinic staff during any routine well-child visits or written communication up to 2 months of life. Clinics will encourage dyads to enroll prior to the child's first month of life to optimize the time that the skin barrier is protected. Eligible dyads may enroll in the study up until infant age 2 months (63 days). Clinic staff will provide interested parents with a tablet computer, a recruitment rack card or recruitment postcard with enrollment URL and QR code.

Recruitment materials will be provided in clinic waiting rooms, clinic examination rooms, enrollment kiosks, through the mail, or via patient portal depending on clinic workflows during child or mother scheduled well visits. All screening and enrollment procedures will be performed online either in the office via computer tablet (e.g. iPad) or via internet-enabled phone or home computer. The electronic consenting process follows all IRB requirements for electronic consent.

Parents will be asked to review a study information sheet and consent to screening procedures. Those who agree will provide their primary contact information and answer a brief screening questionnaire to determine eligibility. Automated data checks will confirm eligibility via inclusion and exclusion criteria. Eligible dyads who wish to continue will be directed to review the consent form. Participants may complete the consenting procedure and enrollment questionnaire in clinic or at home. Potential participants lacking an e-mail address will be instructed to contact the research coordinator to proceed with screening and enrollment.

4.4.2 Additional Screening Procedures – Duke University

In addition to procedures described in section 4.4.1, Duke PBRN coordinators may provide recruitment materials to eligible dyads during routine well-child visits or may initiate phone, mail and/or portal outreach to families. All screening and enrollment procedures will continue online.

4.4.3 Additional Screening Procedures – Oregon Health & Science University

In addition to procedures described in section 4.4.1, and in response to impacts from the COVID-19 pandemic, Oregon PBRN coordinators may be granted access to the participating clinic's patient portal to initiate recruitment messages to potentially eligible families. All screening and enrollment procedures will continue online.

4.4.4 Consent and Enrollment

After reviewing the consent, parents will respond to a survey question asking whether they have any questions about the study. Those who have questions will be instructed to call a toll-free number and speak with a research coordinator to review all aspects of the project. The electronic data capture system (REDCap) will generate an e-mail to the study inbox notifying the research coordinator, who will contact the participant directly if a call is not received. After being informed of the study, parents will use the tablet, phone screen or computer mouse to electronically sign their name to the signature-enabled PDF consent form. After the participant has been determined eligible and given consent, eligible dyads will then be directed to complete the enrollment questionnaire and to provide additional contact information, including details for alternate contacts.

Upon completion of the enrollment questionnaire, dyads will be automatically assigned to a study arm using the randomization schedule.

4.4.5 Randomization

Upon randomization, REDCap will send notification, a PDF of informational materials, and a link to a welcome video via e-mail. Dyads randomized to the intervention arm will also complete an electronic survey to select an emollient from the approved list. Key information regarding treatment allocation (e.g. basics of emollient use or current infant skin care practices) will be submitted in the body of the e-mail, with further information available in printed study materials mailed to parents. For dyads that enroll with text message, the randomization notification and electronic survey to select an emollient will be sent via text message.

Dyads will be randomly allocated to the intervention or control arm using permuted block randomization stratified by clinic and parent-reported family history of AD. Stratifying by site will minimize bias from unmeasured clinic population characteristics while stratifying on family history will assure balance between treatment and control groups in regards to the underlying risk of AD, which has been shown to be approximately two-fold higher in this group.⁵³ In setting up the blocks for randomization we will use block sizes of eight and assigned at a 1:1 ratio to either the control or intervention arm. A randomization schedule will be created using a computer-based random number generator.

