1.2 Rationale for a Barrier Approach to Prevention

A greater understanding of the pathogenesis of AD creates an opportunity for a novel approach to prevention. It is now appreciated that skin barrier dysfunction plays a central role in disease pathogenesis. The etiology of this barrier function may vary between individuals. In some cases, defects in skin barrier genes may be the primary driver of skin barrier dysfunction. The seminal work by Irwin McLean's group in Dundee found loss-of-function mutation defects in filaggrin (FLG gene) to be the strongest predictor of AD ever found.⁹ Filaggrin deficiency leads to increased transepidermal water loss (TEWL) prior to eczema development, reduced cutaneous hydration, and an increase in transcutaneous penetration of environmental irritants and allergens thus initiating skin inflammation.^{10,11} While a groundbreaking discovery, FLG mutations do not explain the majority of AD cases in a given population.¹² Thus, skin barrier dysfunction in many cases of AD may be initiated either by other genetic defects in the skin barrier (e.g. corneodesmosin or claudin-1^{13,14}) or by sub-clinical skin inflammation in children with a predisposition to exaggerated immune responses.¹⁵ Some authors suggest modern skin care practices dry out the skin and alone can initiate skin inflammation.^{16,17} Importantly, Irvine and colleagues recently found skin barrier dysfunction in the first 2 months of life to be the strongest predictor of AD development

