provided by the participant. Electronic copies will not be provided to those lacking an e-mail address.

- c. After consent, parents will then be asked to complete the enrollment questionnaire online. Dyads will complete all study screening and enrollment procedures before they are considered enrolled into the trial. Enrollment questionnaire includes the following:
 - Family history of allergies
 - Home environment
 - Skin care practices
 - Demographics
 - Contact information, including alternate contacts

Once dyads complete enrollment procedures, they will be randomized and will receive an e-mail with information about their treatment arm, a PDF of study information and a link to a welcome video. Dyads who are randomized to the intervention arm will be sent a link to a survey to choose from one of five approved emollients, and the emollient will be shipped to their designated address within three business days of receiving the participant's shipping address. Study payment and randomization arm-specific details will also be mailed to all enrolled participants within three business days of receiving the participant's shipping address. Dyads enrolling with only text message options will receive information about treatment arm via text message.

All procedures completed through randomization are considered 'baseline'. Parents who decline to provide consent to participate will be counted to determine refusal rates.

2 Week Followup, 14 days after enrollment

Two weeks after enrollment, a survey sent via e-mail or text message to the participant with instructions related to study arm. Dyads are asked whether they would like to talk with someone about randomization instructions and are directed to contact research staff via a toll-free number or e-mail. Research staff will initiate a phone call to the participant if the participant does not contact the researcher.

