10.4.3 Secondary analyses of primary endpoint

As a sensitivity analysis, we will perform a complete-case analysis using only subjects who have non-missing outcome data in a logistic regression model adjusting for stratification variables as well as covariates that we find to be associated with missing AD status.⁷⁸ The effect of emollient use will be evaluated with a model similar to the primary analysis, but substituting an indicator of regular reported emollient use (≥ 3 days per week) for intervention allocation. In a separate model, we will include a variable for bathing frequency. In the likely case that bathing and emollient use frequency are associated, we will create and test a combined categorical variable. We will return to the primary intervention-effect model and consider additional covariates previously found or suspected to be associated with AD, such as climate, season of birth, pet ownership, bathing frequency, and characteristics of the living environment using a change-in-estimate approach.⁸³ Finally, we will compare clinic-stratified intervention effects on the primary AD outcome and test their equality with a Breslow-Day test; the purpose is to identify 'large' differences where further investigation into potential protocol deviations or other factors may be warranted, and these results will be interpreted with caution.

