5.3. Analysis of Primary Endpoint

For the primary analysis, we contrast the risk of diagnosed atopic dermatitis (AD) by two years of age for the intervention versus control groups under an intention-to-treat (ITT) assumption, analyzing all subjects according to the group to which they were allocated regardless of adherence or group crossover, and imputing missing outcome values using multiple imputation methods. The measure of interest is the ratio of the intervention:control proportions, a relative risk (RR) measure. If emollient use prevents AD, the RR will be significantly smaller than 1.

Estimation of the relative risk will be by log-binomial regression using a generalized linear model with a log link and binomial distribution. A binary indicator variable will represent assigned **study arm** (intervention=1, control=0). The exponentiated coefficient of this variable, $\exp(\beta_1)$, estimates RR. We will test $\beta_1 \neq 0$ at the 0.05 level of significance. If $p < 0.05$, we will consider RR significantly different from 1, meaning that there is strong evidence for the effect of emollient use on AD in very young children.

Stratification variables will also be included in the model to avoid bias in estimates of effects and standard errors. The stratification variables are **family history of atopy in a first-degree relative** and **recruiting clinic**, which will be included as a **random effect**. Because there are 45 recruiting

clinics in the study, clinic cannot be modelled as a fixed effect without losing statistical efficiency. No other baseline characteristics will be included.

Equation 1

$$\log(p[AD_{ij}]) = \beta_0 + \beta_1 Arm_{ij} + \beta_2 FamHx_{ij} + b_j$$

In this model, the variable *Arm* represents assigned **study arm** (intervention=1, control=0) for participant *i* recruited from clinic *j*. The variable *FamHx* represents family history of atopy in a first-degree relative (1/0). The term b_j is a random intercept for the primary care clinics where participants were recruited. The exponentiated intercept coefficient ($\exp(\beta_0)$) represents the cumulative prevalence of AD in the control arm, while $\exp(\beta_1)$ estimates RR.

Alternative strategies could be used to overcome convergence issues. If this model fails to converge, alternatives include substituting a Poisson model with robust variance estimates, providing starting values for estimation in the statistical software, or using an alternative algorithm.

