5.12. Figures and tables

Figure 1: Screening flowchart (separate from CONSORT diagram, Figure 2)

Future questions related to CONSORT figure:

How to include withdrawn from certain activities? (partial withdrawal) Often reach out shortly after randomization b/c unable to fully comply but may be willing to complete questionnaires.

Also variable in how much emollient requested

Figure 2: CONSORT Flow Diagram

[figure not shown]

Figure 3: Follow-up in the randomized/intention-to-treat (ITT) population

Time point	Intervention/Control Responded	Intervention/Control Missed	Intervention/Control Withdrawn
1 (≤ 2 m)	n (%)	n (%)	n (%) of each: D/C, moved, lost
2 (3m)	n (%)	n (%)	n (%) of each: D/C, moved, lost
3 (6m)	n (%)	n (%)	n (%) of each: D/C, moved, lost
4 (9m)	n (%)	n (%)	n (%) of each: D/C, moved, lost
5 (12m)	n (%)	n (%)	n (%) of each: D/C, moved, lost
6 (15m)	n (%)	n (%)	n (%) of each: D/C, moved, lost
7 (18m)	n (%)	n (%)	n (%) of each: D/C, moved, lost
8 (21m)	n (%)	n (%)	n (%) of each: D/C, moved, lost
9 (24m)	n (%)	na	n (%) of each: D/C, moved, lost
Chart review	n(%)	na	n (%) not found, no consent

Time points 1, 5, 9 (gold): Long-form questionnaires; time points 2, 3, 4 and 6, 7, 8 (white): Brief follow-up.

m: months; n: count; %: percent of randomized total in arm; D/C: discontinued, confirmed by study personnel; moved: moved out of area; lost: lost to follow-up without being able to confirm a reason; na: not applicable.

Responded: full or partial response given; Missed: no response at given time point but later response exists; Withdrawn: No response at this or later time contacts (chart review may be complete). The sum of each row should equal the sum of (responded + missed) in the previous row.

Table 4: Planned summaries of study variables

Table Title	Population	Time Point(s)	Endpoint	Endpoint Type	Summary Statistics by Treatment Assignment
Disposition	ITT	Baseline to 24m each 3m	Disposition	Categorical (AD, no AD, lost to follow-up)	Count
Baseline Variables	ITT	Baseline	Age at enrollment	Weeks	n, mean, SD, Median, min, max
			Parental atopy	Binary(Y/N)	p%(x/n)
			Siblings with atopy	Binary(Y/N)	p%(x/n)
			Any parent or sibling with any atopy	Binary(Y/N)	p%(x/n)
			Home location	Categorical (urban, suburban, rural, etc.)	p%(x/n)
			Farm living	Binary(Y/N)	p%(x/n)
			Dog ownership	Binary(Y/N)	p%(x/n)
			Cat ownership	Binary(Y/N)	p%(x/n)
			Probiotic pills	Binary(Y/N)	p%(x/n)
			Dry skin	Binary(Y/N)	p%(x/n)

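### The primary model omits baseline dry skin, a pre-randomisation proxy for early barrier dysfunction; this causes no bias, but prespecifying it could add a little precision at almost no cost

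*Protocol*

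**What the plan says.** Protocol 4.4.5 stratifies randomisation by clinic and family history and states that "stratifying on family history will assure balance between treatment and control groups in regards to the underlying risk of AD". The sentence then goes on to cite a roughly two-fold higher risk in infants with a family history.

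SAP 5.3 fits a log-binomial model with arm, family history of atopy and a random intercept for clinic (Equation 1). Its reason is: "Stratification variables will also be included in the model to avoid bias in estimates of effects and standard errors". It then closes the list: "No other baseline characteristics will be included". Protocol 10.4.1 likewise names only the stratification variables as covariates in the primary model.

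SAP Table 4 lists "Dry skin Binary(Y/N)" among the baseline variables for the ITT population. Protocol 4.4.4 puts the questionnaire before allocation: "Upon completion of the enrollment questionnaire, dyads will be automatically assigned to a study arm using the randomization schedule". Protocol 6.1 adds: "All procedures completed through randomization are considered 'baseline'".

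Protocol 1.2 cites a finding of "skin barrier dysfunction in the first 2 months of life to be the strongest predictor of AD development" and says that this held independently of filaggrin genotype and family history.

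Other places in the plan allow further covariates:
- Protocol 10.4.1 uses risk factors in the imputation of missing outcomes.
- Protocol 10.4.3 and SAP 5.4 (item 2a) add covariates associated with missing AD status to the complete-case analysis.
- Protocol 10.4.3 has a model with bathing frequency, and a secondary search over further covariates "using a change-in-estimate approach".
- SAP 5.9 puts variables associated with missingness into the imputation model or, without imputation, into the main model.

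None of these names dry skin. It is also not among the subgroups in SAP 5.2 or the sensitivity analyses in SAP 5.10.

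**The concern.** Stratification balances the stratifiers. On the protocol's own account, an important part of AD risk acts independently of family history, so balance on family history says nothing about balance on that part. The trial holds a baseline item, unaffected by treatment, that plausibly reflects it, and the SAP rules it out of the primary model.

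Two things are given up. If dry skin predicts AD, adjustment would reduce the standard error of log RR. And if the arms happen to differ on dry skin, the stratification-only estimate carries that difference uncorrected. These are two views of the same chance variation, so they should not be added together. The routes by which other covariates can enter are secondary or depend on the data. A covariate fixed in advance is preferable to one kept because it moves the treatment estimate.

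**Working it through.** **1. Reproduce the plan's sample size.** Inputs from SAP 2.3: risks 24% and 16.8% (RR 0.70), two-sided alpha 0.05, power 80%. With mean risk p = (0.24 + 0.168)/2 = 0.204:

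n per arm = [1.96·√(2p(1−p)) + 0.8416·√(0.24·0.76 + 0.168·0.832)]² / 0.072² = 490.5, so 491 per arm and 982 in total. This matches the SAP. Power at 491 per arm is 80.0%.

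**2. Inputs for the adjustment.** From the documents: family-history risk ratio about 2 (SAP 2.2) and prevalence 40 to 60% (SAP 5.2; 0.50 used). Assumed, because the documents are silent: dry-skin prevalence 10 to 40% and risk ratio for AD 1.0 to 2.5. Dry skin is taken as independent of family history, and the clinic effect is ignored.

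**3. Precision under the log-binomial model.** For cell risk μ and cell count w, the information is Σ w·μ/(1−μ)·xxᵀ. The variance of log RR is the arm element of its inverse, with and without the dry-skin term. Power = Φ(|ln 0.70|/SE − 1.96). Without dry skin, SE = 0.1264 and power is 80.5% at 491 per arm. With it:

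| Dry-skin RR | SE, range over prevalence 10–40% | Variance cut | Power |
|---|---|---|---|
| 1.0 | 0.1264 | 0% | 80.5% |
| 1.5 | 0.1254–0.1259 | 0.9–1.7% | 80.9–81.2% |
| 2.0 | 0.1231–0.1240 | 3.8–5.3% | 82.0–82.6% |
| 2.5 | 0.1198–0.1211 | 8.3–10.2% | 83.8–84.5% |

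The largest gain is at prevalence 20% and RR 2.5: 1 − (0.1198/0.1264)² ≈ 10%. The relative efficiency there is 1.113, equivalent to about 982 × 0.113 = 111 more infants.

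**4. Precision under the robust-variance Poisson fallback of SAP 5.3.** The large-sample sandwich variance gives smaller gains over the same grid: 0 to 6.3%, with power rising from 80.3% to at most 82.8%. Simulation with this model (982 infants, 2,000 trials per scenario) agrees, with variance ratios from 0.991 (prevalence 20%, RR 1.5) to 0.937 (30%, RR 2.5).

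**5. Bias.** In simulation with 491 per arm, the mean RR without and with dry skin was 0.696 and 0.697 (prevalence 20%, RR 1.5), 0.698 and 0.699 (30%, RR 2.0), and 0.702 and 0.702 (30%, RR 2.5). Omission causes no bias.

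**6. Chance imbalance.** The SD of the between-arm difference in dry-skin prevalence d is √(2d(1−d)/491). At d = 0.30 it is 2.9 percentage points. For a dry-skin risk ratio of 2 and half-imbalance h, the RR is multiplied by (1 + 0.30 + h)/(1 + 0.30 − h). A 1-SD imbalance (h = 0.0146) gives 1.023; since ln 1.023 ≈ 0.0225, this is 0.0225/0.1264 ≈ 0.18 of a standard error. At the 95% limit (5.7 points) the factor is 1.045, so 0.70 would read as 0.67 or 0.73.

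**7. The logistic fallback.** SAP 5.9 allows a logistic model under imputation. The odds ratio is not collapsible: over the assumed values with dry-skin RR of at least 1.5, adding dry skin moved it from 0.631 to between 0.612 and 0.628 with no change in the true treatment effect. The RR has no such problem if it is computed from average predicted risks.

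**The case against.** The strongest reply is that nothing here is wrong. A model with the stratification variables alone, fixed in advance, is valid; randomisation protects the RR; and the SAP's closing sentence guards against choosing covariates after seeing the data. All of that stands. Chance imbalance in dry skin is already allowed for in the unadjusted confidence interval.

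Four stronger readings are tempting, and the documents do not support them.

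- *That dry skin is the strongest predictor of AD.* The evidence in Protocol 1.2 concerns barrier dysfunction, and the title of the cited study shows that it was measured by transepidermal water loss. No document reports that parent-reported dry skin at 0 to 2 months predicts AD. Xerosis in the protocol's diagnostic table supports a diagnosis; it is not presented as a baseline predictor.
- *That Protocol 4.4.5 claims balance on all AD risk.* The rest of the sentence ties the risk to family history, and SAP 2.2 speaks of balance on that one factor.
- *That the change-in-estimate search is the only other adjustment.* The plan has several, and the protocol's covariate list for that search is given as examples, so dry skin is unnamed but not excluded.
- *That dry skin is complete for every infant.* Protocol 6.1 does not name it among the questionnaire topics, and SAP 5.9 assures completeness only for arm, family history and clinic.

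It is also fair to say that SAP Table 4 holds other candidates, such as baths per week and prior emollient use. The argument for dry skin is its closeness to the trial's barrier rationale, not a documented ranking.

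**Conclusion.** The point holds as a low-cost improvement, not as an error in the plan. The primary analysis is valid as written. By excluding a baseline item that fits the trial's own rationale, it may forgo a modest gain: at 982 infants, from nothing to about a 10% variance reduction under the log-binomial model (0 to about 4 points of power), and at most about 6% under the Poisson fallback.

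These figures rest on an assumed prevalence of 10 to 40% and an assumed prognostic risk ratio of 1.0 to 2.5. If parent-reported dry skin is not prognostic, the gain is nil. The quantity estimated is unchanged for the RR from a log-link model. Under the logistic fallback that is assured only if the RR is obtained by standardisation.

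**What to change.** Before unblinding:

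- In SAP 5.3, add baseline dry skin (yes/no) to Equation 1 as a prespecified fixed covariate, and amend the sentence that excludes other baseline characteristics.
- In SAP 5.9, include dry skin in the imputation model, and state a simple rule for missing values, for example a missing category or imputation.
- In SAP 5.10, keep the model with stratification variables only as a named sensitivity analysis.
- If the logistic alternative in SAP 5.9 is used, report the RR as the ratio of average predicted risks. Protocol 10.4.1 already describes this calculation, with delta-method intervals.

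Rewording Protocol 4.4.5 to say that stratification balances family history is optional, since SAP 2.2 already says so.

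The cost is a short SAP amendment, one model parameter (two with a missing category) and no new data collection. An extra term may make convergence of the log-binomial model harder, but SAP 5.3 already provides alternatives.
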